6.6 DATA HANDLING METHODS

6.6.1 Missing Data

6.6.1.1 Date Values

In cases of incomplete dates (e.g., AE, concomitant medication, medical history start and/or stop dates), the missing component(s) will be assumed as the most conservative value(s)

possible. For example, if the start date has a missing day value, the first day of the month will be imputed for study day computations (i.e., treatment-emergent status, etc.) unless it is the same month and year (only day missing) or year (day and month missing) as the start date of treatment. In this case, start date of treatment will be used, which assumes treatment emergence. If day is missing for an end date, the last day of the month will be imputed. A similar imputation will be used for missing month dates.

Date imputation will only be used for computational purposes e.g., treatment-emergent status, etc. Actual data values as they appear in the original CRFs will be shown in the data listings.

6.6.1.2 Non-Date Values

Every effort will be made to obtain the protocol-required data for all study assessments that are scheduled for each visit for all enrolled subjects. Missing values for the primary endpoint of Fugl-Meyer scores for post-baseline visits will be imputed using Last Observation Carried Forward (LOCF) for ITT analyses. Subjects with a six-month Fugl-Meyer score but no baseline score will have their six-month Fugl-Meyer score imputed backwards to serve as their missing baseline Fugl-Meyer score. Subjects with no baseline or six-month Fugl-Meyer score will have the mean baseline Fugl-Meyer score for their treatment arm imputed for both their baseline and six-month score.

These same imputation methods will be used for secondary endpoints as well.

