The beneficial effect of 1Hz NBS guided rTMS will be established if a statistically signicantly greater proportion of patients receiving NBS-rTMS attain clinically important improvement in the primary outcome measure than patients receiving sham-rTMS between baseline and 6 months post-treatment. Minimal clinically important improvement is defined as an increase of 5 points on the upper extremity Fugl-Meyer score [Page SJ, et al. 2012].

Secondary Assessments	1. Secondary outcome measures for the study are:					
and	Arm-Research Action Test (ARAT)					
Endpoints:	NIH Stroke Scale (NIHSS)					

Quality of life assessment: EQ-5D questionnaire.

The changes on these scales between baseline and 6 months post-treatment will be determined for both therapy groups and the groups compared to each other.

2. Safety endpoint

To assess safety of study device use, all Serious Adverse Events and Unanticipated Adverse Device Events and Device Related Adverse Events will be recorded and compared between therapy groups..

ABBREVIATIONS

APB	Abductor Pollicis Brevis
CRO	Clinical Research Organization

EDC	Extensor Digitorum Communis
EMG	Electromyography
FDA	Food and Drug Administration
fMRI	Functional Magnetic Resonance Imaging
IRB	Institutional Review Board
MEP	Motor Evoked Potential
MRI	Magnetic Resonance Imaging
MT	Motor Threshold
NBS	Navigated Brain Stimulation
NBT	Navigated Brain Therapy
rTMS	Repetitive Transcranial Magnetic Stimulation
SAE	Serious Adverse Events
SD	Standard Deviation
TMS	Transcranial Magnetic Stimulation

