6.0 ANALYSIS PLAN

The results of functional motor tests at end of rehabilitation (5-10 days post treatment) and at 1, 3 and 6 months after the end of rehabilitation will be compared to the results obtained at baseline to determine the functional recovery if any that has occurred. The results of patients randomized into separate groups will be compared to each other to determine the effect of rTMS.

The primary analysis population will be the intent-to-treat (ITT) population. In addition, a separate analysis will be conducted on the per protocol (PP) population.

Primary outcome measure for the trial is the Upper-extremity Fugl-Meyer score.

The beneficial effect of 1Hz NBS guided rTMS will be established if a statistically significantly greater proportion of patients receiving NBS-rTMS attain clinically important improvement in the primary outcome measure than patients receiving sham-rTMS between baseline and 6 months post-treatment.

The size of the treatment effect will be measured by the odds ratio parameter which is defined as

$$OR = \frac{P_{TRT} / (1 - P_{TRT})}{P_{REF} / (1 - P_{REF})}$$

where P_{TRT} and P_{REF} denote the proportion of subjects with clinically significant change from baseline in Fugl-Meyer score, in the treatment and reference groups respectively.

The null hypothesis is H_0 : OR = 1 and the two-sided alternative hypothesis is H_1 : $OR \neq 1$.

The proportion of responders in each treatment group will be summarized, along with the estimated odds ratio, the 95% confidence interval for OR, and the Wald Chi-square test p-value. The primary analysis will be performed on the ITT, and on the PP population as a sensitivity analysis.

Secondary outcome measures for the trial are ARAT test, , NIHSS, and EQ-5D.

Descriptive statistics will be summarized by treatment and visit. Absolute difference (in points) in improvement will be summarized for both treatment groups between baseline and 5-10 days and 1, 3 and 6 month follow-up visits and the treatment groups compared via a two-way ANOVA.

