6.2 ANALYSIS SCHEDULE

No interim analyses will be performed for efficacy. Final analysis including analysis of safety and efficacy will be performed once 60 subjects have completed the trial (completed visit #24).

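### LOCF is the only stated method for missing 6-month Fugl-Meyer scores; it biases the responder comparison in either direction when loss differs by arm, and no sensitivity analysis tests it

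*Combined protocol and SAP*

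**What the plan says.** Section 6.6.1.2 gives three single-imputation rules.

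- Missing post-baseline Fugl-Meyer scores are "imputed using Last Observation Carried Forward (LOCF) for ITT analyses".
- A patient with a 6-month score but no baseline has the 6-month score "imputed backwards to serve as their missing baseline Fugl-Meyer score".
- A patient lacking both "will have the mean baseline Fugl-Meyer score for their treatment arm imputed for both their baseline and six-month score".

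The section then adds: "These same imputation methods will be used for secondary endpoints as well".

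The primary endpoint is a responder proportion. The Protocol Summary states that "Minimal clinically important improvement is defined as an increase of 5 points on the upper extremity Fugl-Meyer score", and section 6.0 compares the arms on change "between baseline and 6 months post-treatment". Section 6.3 defines ITT as everyone randomised, so each lost patient needs a value. Section 6.0 names one sensitivity analysis, on the per-protocol population. Section 6.1 makes a Bayesian analysis that borrows the NICHE active arm the primary efficacy analysis, keeps the E-FIT-only analysis for robustness, and sends detailed methods to a separate SAP that was not supplied. Section 4.1 allows extra recruitment to offset losses, and section 6.2 sets the timing: "Final analysis including analysis of safety and efficacy will be performed once 60 subjects have completed the trial".

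**The concern.** LOCF treats a score from 5-10 days, 1 month or 3 months after treatment as the 6-month outcome. The trial measures at four time points because function may still be changing, so the carried score can put a patient on the wrong side of the 5-point threshold. If lost patients are counted as responders at a different rate from the one they would have shown at 6 months, the arm with more loss is shifted further, and the comparison moves with no treatment effect behind it.

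The back-copy and arm-mean rules set the change to exactly zero. Such a patient is always a non-responder and adds an invented zero to any mean change.

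For continuous secondaries, including ARAT (tested at 0.025 in section 6.5 because of possible labelling use), forced zeros shrink effects, and treating filled-in values as observed understates uncertainty. At stake is whether the result depends on an assumption about missing data that the supplied text never varies.

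**Working it through.** **The plan's own figure.** Section 6.1 states 81% power with 60 patients. For 84% v 50%, 30 per arm, two-sided 0.05, pooled variance (mean rate 0.67):

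z = [0.34 × √30 − 1.96 × √(2 × 0.67 × 0.33)] / √(0.84 × 0.16 + 0.50 × 0.50) = (1.862 − 1.303) / 0.620 = 0.90, so power is 81.6%.

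The figure reproduces and contains no allowance for missing data. As an outer bound, if 10% of each arm were lost and all counted as non-responders, the rates become 0.84 × 0.9 = 75.6% and 0.50 × 0.9 = 45.0%, and power falls to 68.7%.

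**Bias formula.** Let p be the true 6-month response rate (taken to be the same for dropouts and completers), d the share of an arm that is imputed, and r the chance that an imputed patient counts as a responder. The expected observed rate is p(1 − d) + r·d. With no true effect, the spurious difference (active minus sham) is (d_sham − d_active)(p − r). It is zero under equal loss and changes sign with the direction of the imbalance.

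**Inputs from the documents.** NICHE mean gain 8.1 points, 66% improving, and 65% improving on sham (section 1.1); 30 per arm (section 5.2.3); 5-point threshold (Protocol Summary).

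**Assumptions.** Dropout rates; 60%, 70% and 85% of each patient's 6-month gain present at 5-10 days, 1 month and 3 months; dropouts split equally among no post-baseline score and a last score at each of those three visits; patients with no post-baseline score count as non-responders.

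**Value of r.** SD = (8.1 − 5) / z(0.66) = 3.1 / 0.4125 = 7.52. The mean gain that yields 65% responders is 5 + 7.52 × 0.385 = 7.90. If a fraction f of the gain is present, a carried-forward patient responds with probability Φ((7.90 − 5/f) / 7.52):

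- f = 0.60: 0.477
- f = 0.70: 0.540
- f = 0.85: 0.606

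With a quarter at zero, r = (0 + 0.477 + 0.540 + 0.606) / 4 = 0.406. If every dropout has a post-baseline score, r = 1.623 / 3 = 0.541.

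**Results.** True 65% in both arms; exact binomial probabilities for a chi-square test at 30 v 30; the last column is the one-sided chance of a false win for active.

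| Loss, active / sham | r | Spurious difference | False win for active |
|---|---|---|---|
| 0% / 0% | – | 0 | 2.4% |
| 15% / 15% | 0.406 | 0 | 2.4% |
| 10% / 15% | 0.406 | 0.05 × 0.244 = 1.2 points | 3.0% |
| 10% / 30% | 0.406 | 0.20 × 0.244 = 4.9 points | 5.7% |
| 30% / 10% | 0.406 | −4.9 points | 0.9% |
| 10% / 30% | 0.541 | 0.20 × 0.109 = 2.2 points | 3.6% |
| 10% / 30% | 0 (all non-responders) | 0.20 × 0.65 = 13.0 points | 17.4% |

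The plan tests two-sided. With r = 0.406 and 10% v 30% loss, total two-sided error moves from about 4.8% to 6.6%.

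**Continuous endpoints.** If a patient who would have gained the NICHE mean is given zero change, the mean of a 30-patient arm drops by 8.1 / 30 = 0.27 points.

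**Borrowing.** None of the table covers the Bayesian analysis. One conditional calculation shows why NICHE handling matters. Suppose the 88 borrowed patients had complete data and were fully pooled (assumptions). Equal 15% loss in E-FIT would then leave 15% of sham imputed but only 0.15 × 30 / 118 = 3.8% of pooled active, an imbalance without any difference in dropout.

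**The case against.** **The size rests on assumptions.** The documents give no dropout rate, no difference between arms and no recovery curve. This stands, and it is why the figures run in both directions. The assumed quarter with no post-baseline score matters most: removing it takes 5.7% to 3.6%. Section 6.6.1.2 does not say that a baseline score is carried forward, so counting patients lost before Visit 21 as non-responders is itself an inference.

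**A reader might infer that LOCF favours active.** The documents do not support that. It holds only if sham loses more; equal loss leaves the false-win rate at 2.4% and the reverse imbalance lowers it to 0.9%.

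**A reader might infer that the back-copy and arm-mean rules drive the result.** Section 5.2 places baseline assessment before randomisation, so a randomised patient without a baseline score should be rare. LOCF is the rule that matters.

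**A reader might infer that patients still in follow-up at the 60th completion would be filled in by LOCF.** Section 6.2 fixes when the analysis happens and does not say that ongoing patients are cut off and imputed. The text leaves this open; it does not prescribe it.

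**The supplied text may be incomplete.** Missing-data sensitivity analyses may be in the separate SAP. That limits the claim to the document reviewed, but section 6.6.1.2 is the operative text here, and the per-protocol analysis does not fill the gap.

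**Conclusion.** The concern holds in a limited form. LOCF is the only stated method for a missing 6-month Fugl-Meyer score in the ITT analysis, it extends to the secondary endpoints, and nothing in the supplied text varies the missing-data assumption. Unequal loss biases the responder comparison in a direction that cannot be known in advance. Under the stated assumptions the effect is small for a 5-point gap in loss and roughly doubles the one-sided false-win rate for a 20-point gap against sham. The illustration assumes that dropouts would have responded like completers, and it covers only the E-FIT-only comparison; the effect on the Bayesian primary analysis cannot be computed from the documents. The claim of understated uncertainty applies mainly to the continuous secondaries. This should be corrected, but it does not by itself invalidate the design.

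**What to change.** - **Primary endpoint:** replace LOCF with multiple imputation of the 6-month score from baseline, observed visits, arm and time-since-stroke stratum, then dichotomise at 5 points. Add site only if the model is stable with about 60 patients.
- **Borrowed data:** handle missing scores in the NICHE active patients in the same way, and say so.
- **Sensitivity:** make a delta-adjusted tipping-point analysis the main one, since multiple imputation in its usual form assumes data missing at random. Report non-responder imputation only as a labelled extreme: in the 10% v 30% case it gives 17.4% false wins against 5.7% for LOCF.
- **Continuous secondaries:** use a mixed model for repeated measures.
- **Section 6.6.1.2:** delete the back-copy and arm-mean rules.
- **Section 6.2:** run the final analysis when every randomised patient has completed Visit 24 or left the study, so that no ITT patient still in follow-up is imputed.

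The cost is some SAP rewriting and programming, and slightly wider intervals.

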6.7 SAFETY ANALYSES

The Safety Population will be used for all analysis, summaries, and listings of safety data.

Adverse Events

All reported terms (investigator descriptions) for AEs will be coded using the most recent version of the Medical Dictionary for Regulatory Activities (MedDRA v16.0) and summarized with frequencies and percentages by treatment group, system organ classification, and preferred term.

Note that subjects experiencing AEs are counted at most one time per preferred term and at most one time per system organ class, at the highest recorded severity and causality. Events without recorded relationship or causality are summarized as severe or definitely related.

The number and percentage of subjects in the following categories will be summarized by group and overall: subjects with AE, TEAE, SAE, TESAE, UADE, DRAE, TEAE resulting in study discontinuation, and deaths.

The following tables will also be presented:

- All TEAEs
- SAEs and TESAEs
- TEAEs by severity
- TEAEs leading to premature discontinuation of study treatment.

Separate data	listings	W1II	be	presented	for	all	AEs	and	SAES.
---------------	----------	------	----	-----------	-----	-----	-----	-----	-------

Unanticipated Adverse Device Events (UADE)

A UADE is defined as any AE that is definitely related to the study device. All UADEs will be summarized by System Organ Class and Preferred Term. A listing of UADEs will also be provided.

Device-Related Adverse Events (DRAE)

A DRAE is defined as any AE that is possibly, probably, or definitely related to the study device. All DRAEs will be summarized by System Organ Class and Preferred Term. A listing of DRAEs will also be provided.

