During TMS there is a loud clicking sound from the coil (up to 120-130dB). Single-pulse TMS induces permanent increases of the auditory threshold [Counter et al. 1990] in animals and transient increases in humans [Pascual-Leone et al. 1992], but these changes can be prevented with the use of foam earplugs [Pascual-Leone et al. 1993].

Immunological Changes

Single-pulse stimulation may induce changes in T lymphocyte subset [Wassermann 2000]. In general, these changes have been short-lived (<48 hours) and comparable to changes seen with stress, menstruation or circadian cycles [Wassermann 2000].

Psychiatric changes

Treatment-emergent mania has been reported for low and high frequency rTMS in patients with uni- and bipolar depression [Xia 2008, Rossi 2009] after stimulation of the left prefrontal cortex. Mania has not been reported in any patients or subjects in whom motor cortex has been stimulated as in the present study.

Neurocognitive Changes

A number of studies have examined the effect of TMS on cognitive function. In general, both transient and short-term studies of TMS have failed to demonstrate consistent effects on cognitive function following TMS [Pascual-Leone et al. 1993; Little et al 2000; Wassermann et al. 1996]. TMS can produce desired and undesired, usually within the frame of the experimental design but potentially long lasting, changes. Such effects, which generally follow a single application of rTMS, can be produced by random neural noise or brain signal suppression (Harris 2008), are small and, are considered not to raise particular safety issues by published consensus statement on the safety of rTMS (for review see Rossi et al., 2007c and Rossi 2009).

EMG

There may be a small amount of irritation of the skin from the electrode paste (less than 5% chance). There is no known risk involved in recording EMG activity from these sensors and electrodes.

Headaches

Another risk that has been cited is a higher frequency of experiencing mild headaches, which resolve soon after the procedure. It is speculated that the headaches may be a result of maintaining a fixed position of the head and neck for the duration of the procedure.

Risk of cardiovascular responses to restful sitting

CONFIDENTIAL

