3.2 SECONDARY OBJECTIVES

Secondary outcome measures for the study are:

Absolute change in points on UEFM

Action-Research Arm Test (ARAT)

NIH Stroke Scale (NIHSS)

The changes on these scales between baseline and 6 months post-treatment will be determined for both therapy groups and the groups compared to each other to establish effects of therapy.

Quality of life outcomes:

In addition to the other secondary outcome measures above the patients' quality of life will be assessed using the EQ-5D questionnaire. The change on this scale between baseline and 6 months post-treatment will be determined for both therapy groups and the groups compared to each other to establish effects of therapy on quality of life.

Assessment of safety:

To assess safety of study device use, all Serious Adverse Events, Unanticipated Adverse Device Events and Device Related Adverse Events will be recorded and compared between therapy groups..

4.0 study design

This is a prospective multi-center sham-controlled double-blinded study.

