6.7.2 Use of Safety results in future labeling

A summary of SAE, UADE and DRAE will be included in future labelling of the NBT device.

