7.0 Monitoring and quality assurance

INDEPENDENT MONITORING OF SOURCE DATA AND SAFETY

The data will be collected by staff members (PI, co-investigators and study staff) familiar with the protocol and the TMS technology. The care, safety, and comfort of the subjects will be under the supervision of a physician and therapist at each trial site).

Clinical monitoring

The study sponsor will be responsible for Clinical Monitoring of the study. The Clinical Monitor's responsibilities include maintaining regular contact with the clinical site through telephone contact and on-site visits, to ensure that:

- the trial is conducted according to protocol;
- the Investigational Plan is followed;

- study staff is trained and capable of performing the tasks required from them in a uniform manner at each trial site. The central site (Rehabilitation Institute of Chicago) will provide training for all assessors and therapists. At the beginning of the study and every 6 months during the study all assessors will be trained, certified and/or re-certified for their role. Additional training will be provided to study staff who do not pass the review. Staff members will only be permitted to perform study duties if they have successfully passed their most recent evaluation.

- complete, timely, and accurate data are recorded and submitted;
- problems with inconsistent or incomplete data are addressed;
- complications and unanticipated adverse effects are reported to the IRB and Sponsor;
- the site facilities continue to be adequate to meet the requirements of the study.

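### A UADE is defined only by certainty of device causality, not by whether the event was anticipated, so a safety endpoint meant for labelling is mislabelled

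*Combined protocol and SAP*

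**What the plan says.** Section 6.7 (Safety Analyses) defines two device categories. For the first: "A UADE is defined as any AE that is definitely related to the study device". For the second: "A DRAE is defined as any AE that is possibly, probably, or definitely related to the study device". Each gets a subject count by group, a table by system organ class and preferred term, and a listing.

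The adverse event paragraph of the same section sets a default for incomplete records: "Events without recorded relationship or causality are summarized as severe or definitely related".

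The category has a stated role. Section 3.2 says that "all Serious Adverse Events, Unanticipated Adverse Device Events and Device Related Adverse Events will be recorded and compared between therapy groups", and the Protocol Summary names the same three classes under its safety endpoint. Section 6.7.2 adds: "A summary of SAE, UADE and DRAE will be included in future labelling of the NBT device".

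Section 7.0 expects monitors to ensure that "complications and unanticipated adverse effects are reported to the IRB and Sponsor", but does not define the term. It does define adverse events, serious adverse events, and device failure, malfunction and misuse.

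**The concern.** The name promises a category of device harms that nobody foresaw. The definition delivers those device harms, foreseen or not, whose causality was rated with most confidence. Whether an event was anticipated and how sure the assessor is of its cause are separate questions, and Section 6.7 uses the second to answer the first.

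At stake is the meaning of one row in the safety summary. A reader of future labelling would take that row as the unexpected device effects seen in the trial. As defined, it could contain known effects and omit a new effect rated probable. A count of zero would not mean that no unanticipated device-related event had occurred. With about 30 subjects per arm, a few misclassified events could visibly change the row.

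**Working it through.** The plan has no figure to reproduce and no calculation applies. The check is to apply the definitions by hand and see whether expectedness ever changes the result.

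**Inputs**
- UADE and DRAE definitions: Section 6.7.
- Default for missing causality: Section 6.7, adverse event paragraph.
- Anticipated effects: Section 2.2, which describes among others skin irritation from electrode paste, hearing change, seizure, symptomatic blood pressure reduction, and headache.

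**Classification under Section 6.7**

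| Causality | Described in 2.2 | Not described in 2.2 |
|---|---|---|
| Possible | DRAE only | DRAE only |
| Probable | DRAE only | DRAE only |
| Definite | DRAE and UADE | DRAE and UADE |
| Missing (default read literally) | DRAE and UADE | DRAE and UADE |

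The two columns are identical, so expectedness never affects the outcome. Every UADE is also a DRAE, and the UADE is the definite stratum of that class.

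**Where the table goes wrong for a category called unanticipated**
1. *Described in 2.2, definite.* Section 2.2 puts skin irritation from electrode paste at under a 5% chance, and Section 1.2 lists EMG as a subsystem of the study technology. If such an irritation is rated definite, it is counted as unanticipated although the protocol itself foresees it.
2. *Not described in 2.2, possible or probable.* However novel, the event is missing from the UADE count, table, listing and labelling summary. It remains in the DRAE output and, if serious, in the SAE output.
3. *Missing causality.* The default supplies exactly the grade that is the sole UADE criterion. Section 6.7 does not say that the default feeds the UADE tables, but a programmer following the text in order would probably reach that result.

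**Is it corrected elsewhere?** Section 3.2, the Protocol Summary, Section 6.7.2 and Section 7.0 use the term or a close variant, and none adds an expectedness test. The list in Section 2.2 is not referred to by the definition.

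**What depends on it?** Section 6.7.1 judges safety on SAEs and specifies a chi-square test for them. Section 3.2 promises a between-group comparison of UADEs, but Section 6.7 specifies only descriptive output for them.

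**The case against.** The strongest reply is that little is lost. An unexpected event rated possible or probable is still counted, tabulated and listed as a DRAE. DRAEs are themselves a named endpoint, and they go into labelling beside the UADEs. All adverse events are listed, Section 7.0 has the DSMB assess each one for relationship to device or procedure, and cases are reviewed monthly. No decision rule uses the UADE count. All of this stands. A reader might infer that the plan would miss new device risks, or that its safety conclusion could be wrong. The document does not support either: the omission is confined to the UADE outputs, and the safety criterion rests on SAEs. What the reply leaves open is that the DRAE table mixes expected and unexpected events, and no planned field separates them.

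Headache looks like the obvious example of an anticipated event counted as unanticipated, since Section 2.2 says: "Another risk that has been cited is a higher frequency of experiencing mild headaches, which resolve soon after the procedure". It is a weak one. The same paragraph speculates that the cause is holding the head and neck still, which points to the procedure, and Section 7.0 records relationship to procedure as well as to device. A definite device rating for a mild headache is therefore not the likely case.

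A reader might also take it as settled that a blank causality field creates a UADE. That is a natural inference, not a stated rule. The default is a cautious convention that avoids under-attributing events to the device. Blanks should also be few, because monitors are to resolve incomplete data and the DSMB assesses relatedness for every event. The objection to the default is limited to its possible carry-over into a category about expectedness.

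**Conclusion.** The point holds as a mismatch between a term and its definition. Following Section 6.7 as written gives a UADE count that does not measure unanticipated events, for an endpoint that is to be compared between groups and summarised in labelling. The misclassification runs both ways: anticipated events rated definite come in, and undescribed events rated possible or probable stay out.

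Its size cannot be computed, because the document gives neither the expected number of adverse events by causality grade nor the frequency of missing causality. Its reach is limited to the UADE outputs. The DRAE and SAE reporting and the primary safety criterion are unaffected.

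This rests on two assumptions. First, Section 2.2 is the protocol's statement of what is anticipated. Second, neither the separate statistical analysis plan cited in Section 6.1 nor the DSMB charter cited in Section 7.0, which were not available for this review, replaces the definition. If one does, Section 6.7 must still be reconciled with it.

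**What to change.** Redefine a UADE in Section 6.7 as an adverse event at least possibly related to the device whose nature or severity is not described in Section 2.2. Leave frequency out of the test, because Section 2.2 gives almost no usable rates. Record expectedness when the DSMB makes its existing relatedness assessment under Section 7.0; no additional reviewer is needed.

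If the sponsor still wants the definite-causality stratum, report it under a name that says so. Missing causality may stay conservatively counted as device-related for the DRAE tables, but state that it does not by itself make an event a UADE.

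One consequence should be accepted openly. Section 2.2 describes effects such as seizure and hearing loss as potential risks, so an occurrence within the described nature and severity would leave the UADE table. It would remain a DRAE if rated at least possibly device-related, and an SAE if serious.

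The cost is a wording change and one expectedness field. Sample size, visits and the efficacy analysis are untouched. The change is best made before unblinding.
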